### **3.2.22 Rules and data formats**

Data will be presented using an appropriate number of decimal places (i.e. the number of decimal places used does not imply undue precision). Raw data will be presented with the number of decimal places collected, and derived data will be presented to an appropriate number of decimal places. The appropriate number of decimal places will be determined by general practice, mathematical rationale or scientific rationale (e.g. age should be presented in whole numbers).

For PK/dosimetry data, all values will be reported with 3 significant digits for numbers < 1000, otherwise values will not be rounded.

For summary statistics, the following will be presented: n, arithmetic mean, standard deviation, median and the range (minimum, maximum).

Mean, median and standard deviation values will be reported with one decimal place greater than the raw/derived data that they summarise. Minimum and maximum values will be reported with the same precision as the raw data.

Percentages will be reported with 1 decimal place and 0% will not be presented. Percentages will be calculated using a denominator of all subjects in a specified population and by treatment group. The denominator will be specified in a footnote to the tables for clarification if necessary.

All values below or above a limit of quantification (e.g. < 0.1 or > 100) will be listed as such. For each safety parameter for which it is possible to have values below or above LOQ, the rule to be used in the statistical tables is to replace values below or above a limit of quantification by LOQ.

All text fields must be left justified and numeric or numeric with some text specification (e.g. not done, unknown, < 4.5, ...) must be decimal justified. Dates will be presented in the format [yyyy-mm-dd] and times in the format [hh:mm].

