### 2.3 **Safety population**

The safety population is all subjects who received at least one dose of study medication (including screening administration).

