## **3.2 Analysis methods**

### **3.2.1 Safety**

All safety data will be included in the data listings and summary tables will be based on the safety population.

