A TEAE for the long-term follow-up period is defined as any AE that occurs during the long-term follow-up period of the study if:

- It was not present prior to EOCT/ED visit or EOAC/ED visit, or
- It was present prior to EOCT/ED visit or EOAC/ED visit but the grade increased between EOCT/ED visit or EOAC/ED visit and end of study,
- It was present prior to EOCT/ED visit or EOAC/ED visit, the grade is the same but the causality changed to “related” between EOCT/ED visit or EOAC/ED visit and end of study.

In addition, adverse events will be assigned to a specific cycle of treatment for core trial and additional cycles. This assignment will be based on the start date of the adverse event: if the AE start date is on or after the date of treatment X and before the date of treatment X+1 (or if the subject does not receive a treatment X+1 or the treatment X+1 date is missing), then the TEAE will be assigned to Treatment Cycle X.

An overall summary table of all AEs will be presented by treatment group and overall, by cycle (if applicable) and overall, after IMP screening administration, for core trial, additional cycles and follow-up long term separately. In addition, an overall summary table will be presented by pooling cycles from core trial and additional cycles.

TEAEs will be summarised by treatment group and overall with the number and percentage of subjects with AEs classified by primary system organ class and preferred term, by cycle (if applicable) and overall, after IMP screening administration, for core trial, additional cycles and follow-up long term separately. The number of occurrences of a TEAE will also be presented.

In addition, summary tables will also be presented for related TEAEs, SAEs, related SAEs, non-serious TEAEs, TEAEs by decreasing frequency, TEAEs by NCI-CTCAE worst grade (for NCI-CTCAE worst grade  $\geq 3$ ) and TEAEs by most serious causality (category related only).

Summary of TEAEs and related TEAEs will be also summarised by pooling cycles from core trial and additional cycles.

DLTs during cycle 1 or 2 (i.e. occurring between the first administration of Lu-3BP-227 and EOCT/ED) will be summarised by treatment group and overall with the number and percentage of subjects with DLTs classified by primary system organ class and preferred term. The number of occurrences of a DLT will also be presented.

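### SAP safety percentages use denominators that include subjects not at risk: screening-only subjects in the pooled core-trial column, and subjects who never started the cycle or period in the by-cycle and by-period columns

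*SAP*

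**What the plan says.** Three SAP rules act together.

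- Section 2.3 makes the safety population "all subjects who received at least one dose of study medication (including screening administration". A subject who received only the screening dose is therefore a member. Section 2.7 names this the primary population.
- Section 3.2.1 adds that "summary tables will be based on the safety population".
- Section 3.2.22 fixes the divisor: "Percentages will be calculated using a denominator of all subjects in a specified population and by treatment group". The sentence after it reads "The denominator will be specified in a footnote to the tables for clarification if necessary".

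Section 3.2.1.1 then asks for TEAE numbers and percentages per treatment group and pooled, "by cycle (if applicable) and overall, after IMP screening administration, for core trial, additional cycles and follow-up long term separately". DLTs are to be "summarised by treatment group and overall with the number and percentage of subjects with DLTs". Section 3.2.1.2 adds worst laboratory grade by cycle.

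The SAP also defines an included population of subjects who received the therapeutic dose (section 2.2). It uses that set for overall survival, baseline characteristics, withdrawals and concomitant medication, but not for safety. Protocol 12.1 defines a set for MTCA and MTSA evaluation: subjects who finish Cycle 2 or stop in Cycle 1 or 2 because of a DLT. The SAP does not carry that set over, and its section 5 declares no changes from the protocol.

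**The concern.** The numerators are restricted by period and cycle, but the denominators are not. Under SAP 3.2.1.1 a core-trial TEAE needs a first core-trial dose, and an event belongs to Cycle X only if it starts on or after that cycle's treatment date. A screening-only subject cannot have a core-trial TEAE or a DLT in Cycle 1 or 2. A subject who never started Cycle 2 cannot have a Cycle 2 event. The visible rule nevertheless counts both.

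Screening-only subjects are expected: protocol 6.2.1.2 gives them their own discharge checks and safety follow-up. The reverse mismatch also occurs. Inclusion criterion 5(b) admits subjects on 111In uptake from another study, and the rationale for Amendment 7 says they need no 177Lu screening dose. Once treated, they belong to the safety population and so to the divisor of the screening-dose table.

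Safety and tolerability are the primary objective. By-cycle tables are where toxicity rising with cumulative activity would show, and fewer subjects remain at risk in later cycles and periods. SAP 3.2.24 also names an outside use: the cohort 2 safety tables will support the starting dose of a combination study.

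**Working it through.** The documents print no incidence to reproduce, so the check is a set of plain ratios.

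**1. Pooled core-trial column.** Treated subjects: 30, the planned maximum (SAP 1.2). Screening-only subjects: s, unknown because the planned number screened is blacked out. For x subjects with an event,

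printed percentage = x/(30+s) = (x/30) × 30/(30+s).

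| s (assumed) | 30/(30+s) | 6 with a DLT (20.0% of treated) | 10 with a DLT (33.3% of treated) |
|---|---|---|---|
| 5 | 0.86 | 17.1% | 28.6% |
| 10 | 0.75 | 15.0% | 25.0% |
| 15 | 0.67 | 13.3% | 22.2% |
| 30 | 0.50 | 10.0% | 16.7% |

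The event counts are illustrative.

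**2. Cohort columns, whole core trial.** SAP 3.2.22 divides by treatment group. Taking that to mean the activity cohort, a screening-only subject has none. These columns are therefore not diluted by such subjects.

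**3. Cycle 2 columns.** The dilution factor is the number starting Cycle 2 divided by the number treated. Protocol Table 13 gives simulated mean numbers for both cycles. The last column applies the factor to an illustrative 33.3% among those who started Cycle 2.

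| Scenario | Cycle 1 | Cycle 2 | Ratio | 33.3% would print as |
|---|---|---|---|---|
| A Safe | 17.5 | 15.7 | 0.90 | 29.9% |
| B Late | 17.7 | 15.7 | 0.89 | 29.5% |
| C Early | 18.7 | 14.3 | 0.76 | 25.5% |
| D Toxic | 9.1 | 3.6 | 0.40 | 13.2% |
| E Peak | 15.9 | 10.8 | 0.68 | 22.6% |

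These are ratios of means over all cohorts, before any screening-only subject is added to a pooled column.

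For a single cohort, take the maximum of 5 treated and the minimum of 3 reaching Cycle 2 (SAP 1.2). One event is 1/3 = 33.3% of those at risk but prints as 1/5 = 20.0%. This needs no redacted number.

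**4. Additional cycles, pooled.** Assume 10 of 30 subjects enter and 3 have the event. Among those who entered, 3/10 = 30.0%. Over all treated, 3/30 = 10.0%. With s = 15 as well, 3/45 = 6.7%.

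**5. Screening-dose table.** Screening-only subjects belong here. Subjects admitted under criterion 5(b) without the screening dose do not, yet they are counted. Their number is not given, so no factor can be computed.

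**The case against.** The strongest defence is that the SAP follows the protocol, since protocol 12.1 also defines the safety set as everyone with at least one dose of IMP. Dividing Cycle 2 or additional-cycle events by all treated subjects is a legitimate cumulative incidence. Dividing by those who entered conditions on a selected group, because additional cycles require clinical benefit and acceptable tolerability. That stands as an argument for labelling. It does not justify screening-only subjects in a core-trial divisor.

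A second defence is that the footnote sentence, or table shells in the blacked-out appendix pages, may set other denominators. The footnote provision only clarifies a denominator and does not authorise a different one. Shells that cannot be seen do not displace a visible rule, although they could soften its effect.

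Four stronger readings are tempting and are not supported:

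- A reader might infer that every safety percentage, including cohort DLT rates, is diluted by screening-only subjects. The treatment-group clause in 3.2.22 rules that out for whole-core-trial cohort columns. The by-cycle table of DLT or Grade ≥2 events asks only for numbers.
- A reader might infer that dose finding is biased. MTCA and MTSA have their own set in protocol 12.1, escalation uses counts and the Bayesian model in protocol 19.5, and the SRC reviews all cumulative data.
- A reader might conclude that cycles cannot be compared. Counts, disposition, visit attendance and number of cycles are all tabulated (SAP 3.2.1.1, 3.2.3, 3.2.13), so rates can be recomputed.
- A reader might try to size s from the NTSR1 expression rates in protocol 1.7. Those are tissue findings, not the share of subjects whose uptake an investigator judges above background.

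**Conclusion.** The point holds for two kinds of column and one table. The pooled core-trial TEAE and DLT percentages are too low by 30/(30+s), a size that stays open because s is not visible. By-cycle, additional-cycle and follow-up TEAE percentages, within cohorts as well as pooled, are too low as rates among subjects at risk. The same applies to worst laboratory grade by cycle if it is shown as a percentage. On the protocol's simulated numbers the Cycle 2 factor runs from 0.40 to 0.90. The screening-dose table counts some subjects who never had that dose.

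This rests on a literal reading of SAP 2.3, 3.2.1 and 3.2.22, and on treatment group meaning activity cohort. The consequence is understated incidence in the tables for the primary safety objective. For cohort 2 it is confined to the by-cycle and later-period columns that feed the other study's rationale. It does not reach the MTCA, MTSA or SRC decisions.

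**What to change.** Amend SAP 3.2.1 and 3.2.22 to state denominators by table:

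- core-trial TEAE and DLT tables: the included population (at least one therapeutic dose);
- by-cycle columns, including worst laboratory grade: subjects dosed in that cycle;
- additional-cycle and follow-up tables: subjects who entered the period, labelled as conditional on entry;
- screening-dose table: subjects who received the 177Lu screening dose.

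Add the protocol 12.1 DLT-evaluable set to SAP section 2 and use it for DLT rates that are to be read against the 33% limit.

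The cost is SAP wording and table programming, with no new data. The drawback is that denominators will differ between columns, so each table must print its N per column.

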### **3.2.23 Pooling of Centres**

It is not planned to perform a subgroup analysis on individual or groups of centres.

### 3.2.24 *Interim analysis*

An interim analysis of the escalation cohort data will be done at the end of the core trial. In addition, tables of safety and efficacy data from cohort 2 (4 GBqx2) will be used to support the rationale for the starting dose of  $^{177}\text{Lu}$ -IPN01087 in phase I study combination with Chemotherapy (Gemcitabine-Nab paclitaxel).

### 3.2.25 *Role of Safety Review Committee (SRC)*

During the dose escalation part and before each decision on further dose escalation, safety and dose limit organ exposure data will be summarised and presented to the SRC. This SRC will be set up for the dose escalation decisions (after the end of the third subject's Cycle 1) and second dosing cycle (after the end of the third subject's Cycle 2).

At the time of SRC meeting, all cumulative available information will be reviewed.

A continual reassessment method (CRM) in conjunction with a Bayesian approach modeling of DLT rates and radiation exposure to target organs may be performed during the planned review meetings to generate additional relevant information for the adaptive dose selection decisions. PK and pharmacodynamic data may be also incorporated in the model. The SRC will review all available data and make the final decision as to dose escalation, de-escalation, or cohort expansion during the adaptive dose-escalation phase. This group will also determine when to implement predefined stopping rules.

A specific charter has been developed to define roles and responsibilities, as well as the data set to be reviewed by the SRC.

### 3.2.26 *Covariates and analysis of subgroups*

It is not planned to perform an analysis of subgroups or use covariates.

## 4 **COMPUTER SYSTEMS, SOFTWARE AND VALIDATION OF PROGRAMS**

### 4.1 **Hardware**

The statistical analysis will be performed using Microsoft Windows 7 Enterprise.

### 4.2 **Software**

All TFLs will be produced and statistical analysis performed using SAS version 9.4 [2]. All outputs will be in Microsoft Word Format and compiled in bookmarked .pdf files as per ICH section (e.g. 14.1, 14.2 ...).

### 4.3 **Validation programs**

Biotrial Biometrics will provide a validation plan to Ipsen identifying the methods of validation.

The study statistician is responsible for reviewing each output associated with the deliverable product. Program logs are checked by the statistical programmer for logical, syntax and fatal errors. The checks in SAS includes, but is not limited to, all ERRORS, WARNINGS, BY-VALUE merge messages, NOTES, and UNINITIALIZED variables. Program logs are also reviewed for accurate and consistent variable and observation counts following each procedure and data step.

The study statistician is responsible for checking and reviewing the work produced using whatever method he/she feels is appropriate (e.g. SAS code review, hand calculation, etc.) to reassure of the quality of the output.

Outputs are reviewed for typographical errors, misspellings and nonsensical values or results and to check the consistency with the statistical analysis plan. Outputs are

cross-checked against each other for accuracy and consistency. For statistical tables, listings, appendix listings, and figures, this procedure includes comparison of subject group numbers, counts of subjects at each observation point, and consistency of results for variables between outputs.

Findings of the quality control reviews are communicated to the party responsible for making necessary changes. The programs will be retested after modifications.

After final review, and when no further change is required to produce the deliverable, the statistical programmer and the study statistician have to complete and sign the quality control and statistical analysis results follow-up's validation checklist, to indicate that they have successfully performed all of their responsibilities. Copies of the internal quality control forms produced for the validation process will be provided to the sponsor to support the validation.

#### **4.4 Restitution of the programs**

All programs (including macros and analysis datasets) producing the tables, listings and statistical outputs along with associated logs should be given to the sponsor when the TFLs and statistical analyses have been finalised.

### **5 CHANGES FROM PROTOCOL**

Not applicable.

## 7 APPENDICES TO THE SAP

### Appendix 1: Derived Data

The following derived data will be calculated:

- Study day

Study day will be defined as ‘-1’ for the day prior to first IMP administration during core trial and as ‘1’ for the day of first IMP administration during core trial (i.e. day 0 does not exist).

- BMI

BMI (kg/m^2) will be derived as  $\text{Weight (kg)} / [\text{Height(cm)} / 100]^2$  and rounded to the nearest decimal.

- Core trial duration

Core trial duration (days) will be calculated as (date of last visit attended during core trial - date of informed consent form) + 1.

- Long-term follow-up duration

Long-term follow-up duration (days) will be calculated as (date of last visit attended during long-term follow-up - date of informed consent form) + 1.

- Time since diagnosis

Time since diagnosis in months will be calculated as (date of informed consent form - date of diagnosis) + 1] / 30.4375.

- Time since first relapse after last treatment

Time since first relapse after last treatment in months will be calculated as (date of informed consent form - date of first relapse after last treatment) + 1] / 30.4375.

- Baseline

Baseline will be derived as the last available (and reliable if applicable) assessment before first IMP administration.

- Changes from baseline

Changes from baseline will be calculated as the difference from baseline (e.g. assessment at the visit – assessment at baseline).

- Duration of each cycle

Duration of each cycle (days) will be calculated as (date of infusion of the next cycle - date of infusion of the cycle) + 1.

For last cycle, duration will be calculated as (date of Day 29 of last cycle - date of infusion of the cycle) + 1.

- Study drug exposure during core trial

Study drug exposure (days) = (date of infusion of last cycle during core trial - date of infusion of cycle 1) + 29 days.

- Study drug exposure during additional cycles

Study drug exposure (days) = (date of infusion of last cycle during additional cycles - date of infusion of first cycle during additional cycles) + 29 days.

- Progression-Free Survival

PFS time (weeks) = [(Date of event – date of first treatment administration) + 1] / 7.

Event	Decision	Date of event or censoring to consider for the analysis
Progression Disease	Not censored	Date of progression
No event	Censored	Last date of tumour assessment
Death	Not Censored	Date of death

- Overall survival

$OS\ time\ (weeks) = [(Date\ of\ death\ or\ last\ date\ know\ to\ be\ alive - date\ of\ first\ treatment\ administration) + 1] / 7.$

Event	Decision	Date of event or censoring to consider for the analysis
Death	Not censored	Date of death
No event	Censored	Date last known to be alive

- Therapeutic Class

The therapeutic class will correspond to the first three digits of the ATC code. The decoding of the therapeutic class will be done from the WHO-DD (latest version at the time of database lock).

- Prior and concomitant flags

The date and time of baseline (study day 1) is used as the cut-off date for the definition of prior and concomitant medications. A medication started before study day 1 and continuing at time of Day 1 is considered as both, prior and concomitant. Prior, concomitant and both prior and concomitant will be coded as P, C and PC respectively.

In the event of incomplete start date and/or stop date which will not allow the categorisation of medication, it will be considered as concomitant.

- Medical and surgical history

The duration of medical and surgical history will be calculated as (end date – start date) + 1. If the recorded end date is CONT. (for continuing), the end date will be listed as “ongoing” and the duration will be approximated as “≥ (screening visit date – start date) + 1” day(s). If the start date or the end date are partial, the duration will be presented as a superior inequality “≥ xx”day(s) [i.e. ≥2 where start date=31JAN2004 and end date=FEB2004 or start date=JAN2004 and end date=01FEB2004] but if both are partial or one is missing the duration will not be presented.

- Prior and concomitant medication/Concomitant medications for studied disease /prior and concomitant non-drug therapies duration

If the start and end dates of the medication are identical then “<1” day will be presented with the duration in hh:mm recorded in the eCRF if it is available. If times are available, the duration of treatments will be calculated as (end date/time - start date/time). If at least one time is missing, the duration of concomitant treatments will be calculated as (end date - start date) + 1. If the recorded end date is continuing at the end of the study then the end date will be listed as “ongoing” and the duration will be approximated as “≥(last attended visit date – start date) + 1” day(s). If the start date or the end date are partial, the duration will be presented as an inequality “≥xx” day(s) [i.e. ≥2 where start date=31JAN2004 and end date=FEB2004 or start date=JAN2004 and end date=01FEB2004] but if both are partial or one is missing the duration will not be presented.

- AE duration

If the start and end dates of the AE are identical then “<1” day will be presented with the duration in hh:mm recorded in the eCRF if it is available. If times are available, the duration will be calculated as (end date/time – start date/time) and presented in days hh:mm. If at least one time is missing and if the duration is greater than 24 hours then it will be calculated as (end date - start date) + 1 and presented in days. If the recorded end date is continuing at the end of the study, the end date will be listed as “ongoing” and the duration will be approximated as “≥(last attended visit date – start date) + 1” day(s). If the start date or the end date are partial the duration will be presented as a superior inequality “≥xx” day(s) [i.e. ≥2 where start date=31JAN2004 and end date=FEB2004 or start date=JAN2004 and end date=01FEB2004].

- Time since last dose for adverse event

If the start date of the adverse event is identical to the date of last administration, then “<1” day will be presented with the duration in hh:mm recorded in the eCRF if it is available. Otherwise, it will be calculated as (start date/time - last administration date/time) and presented in days days hh:mm. If at least one time is missing and if the duration is greater than 24 hours then it will be calculated as (start date – last administration date) + 1 and presented in days. If the start date and the associated information do not allow to state about the last dose received (partial start date or start at administration day without knowing if it started before or after the drug intake), all the possible time since last dose will be presented [i.e.: if a subject received a daily administration and reported an AE at second administration day but without indication about before or after the drug intake the time since last dose will be as “2 / <1”]. If the start date is partial, the time since last dose will be presented as an superior inequality (i.e.: for an AE started in FEB2004 after the only administration performed on 31JAN2004, the time since last dose will be as “≥2” days). If the start date is missing the time since last dose will not be presented although the AE will be assigned to each dose received before its end date.

CCI

CCI

CCI

CCI

CCI

CCI

CCI

CCI

CCI

CCI

CCI

CCI

CCI

CCI

CCI

CCI

CCI

CCI

[figure not shown]

CCI

CCI

CCI
